***Example***

	Dose 2 – previous studies	Month 0- current study BS	Time since vacc 2	Assigned time frame for the Month 0 blood sample	Assigned time frame for the year 1 blood sample	Assigned time frame for the year 2 blood sample	Assigned time frame for the year 3 blood sample
pid 1	1-nov-11	2-feb-16	4,260273973	4	5	6	7
pid 2	1-nov-11	5-jul-16	4,682191781	5	6	7	8

***6.3.3.1. Humoral immune response***

For the yearly prediction of the GMCs (year 5 to year 10 and beyond): the analysis of Ab persistence will be based on the ATP cohort for persistence adapted for each year. ***The methodology of modelling prediction is mentioned in Section 7.4.3.***

In order to assess the persistence at Year 5, 6, 7, 8, 9 and 10 and beyond after the primary vaccination in the ZOSTER-006/022 studies, a longitudinal analysis will be performed and will include all results from ZOSTER-006/022 studies and all results from this ZOSTER-049 study.

The following parameters will be tabulated by vaccine group for all timeframes:

- Seropositivity rate with exact 95% CI;
- GMC with 95% CI;
- Vaccine response rate with exact 95% CI;
- MGI from baseline with 95% CI for anti-gE;
- The distribution of Ab titres will be tabulated and also presented using reverse cumulative curves.

Note that the baseline that will be used for the computation of MGI and VRR will be the concentration obtained at pre-vaccination in the primary studies.

***6.3.3.2. Cell-mediated immune response***

For the yearly prediction of the GMCs (year 5 to year 10 and beyond): the analysis of CMI persistence will be based on the ATP cohort for persistence adapted for each year. ***The methodology of modelling prediction is mentioned in Section 7.4.3.***

In order to assess the persistence at Year 5, 6, 7, 8, 9 and 10 and beyond after the primary vaccination in the ZOSTER-006/022, a longitudinal analysis will be performed and will include all results from ZOSTER-006/022 studies and all results from this ZOSTER-049 study.

The following parameters on the frequency of CD4+ T-cells secreting at least two activation markers (from among IFN- $\gamma$ , IL-2, TNF- $\alpha$ , CD40L) for gE-specific stimulation will be tabulated by group for all timeframes.

- Descriptive statistics (N, mean, SD, min, Q1, median, Q3, max)
- Vaccine response rate with exact 95% CI.

Note that the baseline that will be used for the computation of VRR will be the concentration obtained at pre-vaccination in the primary studies.

#### 6.3.3.3. **Additional consideration**

*Following analysis will be performed by age strata (50-59, 60-69,  $\geq 70$  and  $\geq 60$  YOA at primary vaccination), gender, race, ethnicity and region for HI:-*

- *Seropositivity rate and GMC with exact 95% CI;*
- *VRR over pre-vaccination in the primary ZOSTER-006/022 studies with exact 95% CI;*
- *MGI from baseline with 95% CI*

*Following analysis will be performed by age strata (50-59, 60-69,  $\geq 70$  and  $\geq 60$  YOA at primary vaccination), gender, race, ethnicity and region for CMI:-*

- *Descriptive statistics (N, mean, SD, min, Q1, median, Q3, max) of the frequency of CD4+ T-cells secreting at least two activation markers (from among IFN- $\gamma$ , IL-2, TNF- $\alpha$ , CD40L) for gE-specific stimulation will be presented*
- *CMI Vaccine response rate with exact 95% CI.*

### 6.4. **Analysis of safety**

#### 6.4.1. **Analysis of safety planned in the protocol**

The analysis will be performed on the TVC.

The results for the analysis of safety will be tabulated as follows:

- The percentage of subjects with at least one local solicited AE, with at least one general solicited AE and with any solicited AEs during the solicited 7-day follow-up period will be tabulated with exact 95% CI after each vaccine dose and overall (1- Additional Dose and Revaccination groups). The same tabulation will be performed for grade 3 solicited adverse events;
- The percentage of subjects reporting each individual solicited local and general AE during the solicited 7-day follow-up period will be tabulated with exact 95% CI (1- Additional Dose and Revaccination groups). For all solicited symptoms, the same tabulation will be performed for grade 3 solicited AEs, grade 3 related, **medically attended** and for solicited general AEs with **causal** relationship to vaccination (1- Additional Dose and Revaccination groups);

- The percentage of subjects reporting temperature by half degree (°C) cumulative increments. Similar tabulations will be performed for any fever with a causal relationship to vaccination and for any fever resulting in a medically attended visit (1-Additional Dose and Revaccination groups);
- The percentage of subjects with at least one report of unsolicited AE classified by the MedDRA Preferred Terms and reported up to 30 days after each vaccination will be tabulated with exact 95% CI (1-Additional Dose and Revaccination groups). *The same tabulation will be performed for grade 3 unsolicited AEs, for unsolicited AEs with a relationship to vaccination and grade 3 unsolicited AEs related to vaccination;*
- The percentage of unsolicited AEs resulting in a medically attended visit will also be tabulated (*Control, 1-Additional Dose and Revaccination groups. The table for medically attended unsolicited adverse events will be presented within 30 days post each vaccination for 1-Additional Dose and Revaccination group and within 30 days post Month 0 and Month 2 visit for Control group. The medically attended unsolicited adverse events will also be presented from first vaccination up to 6 months post last vaccination for 1-Additional Dose and Revaccination group and within 6 months of Month 0 visit for Control group.*
- Total number/percentages of doses (per dose and overall) followed by *unsolicited* AEs will be tabulated (1-Additional Dose and Revaccination groups);
- Number of subjects with pIMDs and SAEs will be tabulated (1-Additional Dose, Revaccination and Control groups). *The table will be presented within 30 days post each vaccination for 1-Additional Dose and Revaccination group and within 30 days post Month 0 and Month 2 visit for Control group. The pIMDs and SAEs will also be presented from first vaccination up to 12 months post last vaccination for 1-Additional Dose and Revaccination group and within 12 months of Month 0 visit for Control group; The same will be presented for pIMD and SAEs causally related to vaccination for 1-Additional and Revaccination groups.*
- *Number and percentage of subjects with SAEs reported related to investigational vaccine, related to study participation or concurrent GSK medication/vaccine will be presented till end of the study for all groups.*
- *Listing of SAEs from first vaccination up to 12 months post last vaccination for 1-Additional dose and Revaccination group and within 12 months of Month 0 visit for Control group*
- *Listing of all SAEs and all pIMDs (all groups) collected in the Expedited AE form*
- *Listing of SAEs related to study participation or to GSK concomitant medication/vaccine (all groups);*
- *Listing of Adverse events (AEs)/SAEs leading to withdrawal from the study (all groups);*
- *Listing of HZ complications (all groups).*

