Pre-Vacc = Pre Vaccination; Post Vacc 1 = Post Vaccination 1; Post Vacc 2 = Post Vaccination 2; Ab = Antibody; HI = Humoral Immunogenicity; CMI = Cell-Mediated Immunity; mL = Millilitre; pIMDs = potential Immune-Mediated Diseases; IMC = Intercurrent Medical Conditions; SAE = Serious Adverse Event; GSK = GlaxoSmithKline; HZ = Herpes Zoster.

† Visit Month 2 for Vacc 2 is only for the Revaccination group.

‡ Visit Month 3 for blood sample is only for the Revaccination and Control groups.

a After Visit Month 3 (After Visit Month 1 for the 1-Additional Dose group), monthly phone contacts between the subjects and the investigator and/or his delegate will be scheduled for the subject to respond to a standard set of questions, in a language that is understandable to the subject, to collect information on safety, on the occurrence of HZ, and to follow-up ongoing HZ cases (see Section 6.3.1.1). The Control group will also have a phone contact at Visit Month 2. Monthly contacts will occur after Visit Month 3 until the subject's last visit, except at months that coincide with the subject's scheduled visits.

b The study procedures applicable for the Visit Year 1 to Visit Year 6 are identical (except Visit Year 6 is the Study Conclusion).

c Refer to Section 6.5.11.

d Only applicable for females of childbearing potential. A urine pregnancy test is sufficient. A serum pregnancy test instead of a urine pregnancy test should only be considered if required by country, local or ethics committee regulations (see Section 6.5.5).

e Subjects/ subject's caregiver will be instructed to contact their study site immediately if he/she develops any symptoms suggestive of HZ and/or, if he/she manifests any symptoms he/she perceives as serious.

f A study procedure only for the two groups vaccinated with 1 or 2 additional doses of HZ/su vaccine (1-Additional Dose and Revaccination).

g The reporting of medically attended visits will be from Visit Month 0 until 6 months (for the Control and 1-Additional Dose groups) and from Visit Month 0 until 6 months after last HZ/su vaccination (for the Revaccination group) (see Section 9.1.5 and Table 26).

h The reporting of all SAEs and pIMDs will be from Visit Month 0 until 12 months (for Control and 1-Additional Dose groups) and from Visit Month 0 until 12 months after last HZ/su vaccination (for the Revaccination group) (see Table 26).

i E-sign off at year 2 and year 4 for the year 2 and year 4 analyses (for the Control group, only).

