**Table 9 Intervals between study visits for the 1-Additional Dose and Control groups**

Interval between Visits	Optimal length of interval (in months) 	Allowed interval (range in days)
Visit Month 0 → Visit Month 1	1 month	28 – 48 
Visit Month 0 → Visit Month 3 *	3 months	75 – 105 
Visit Month 0 → Visit Year 1	12 months	335 – 395 
Visit Month 0 → Visit Year 2	24 months	700 – 760 
Visit Month 0 → Visit Year 3	36 months	1065 – 1125 
Visit Month 0 → Visit Year 4	48 months	1430 – 1490 
Visit Month 0 → Visit Year 5	60 months	1795 – 1855 
Visit Month 0 → Visit Year 6 4	72 months	2160 – 2220 3

\* Interval ONLY for the Control group.

 Whenever possible the investigator should arrange study visits within this interval.

 Subjects may not be eligible for inclusion in the ATP cohort for analysis of immunogenicity if they make the study visit outside this interval.

 Subjects may not be eliminated from the ATP cohort for analysis if they make the study visit outside this interval.

 For subjects in HZ follow-up at the time of their last yearly visit, their Study conclusion will coincide with their last Day HZ-91 visit (see [Table 11](#)).

**CONFIDENTIAL**201190 (ZOSTER-049 EXT:006-022)  
Protocol Amendment 5 Final**Table 10 Intervals between study visits for the Revaccination group**

Interval between Visits	Optimal length of interval (in months) 	Allowed interval (range in days)
Visit Month 0 → Visit Month 1	1 month	28 – 48 
Visit Month 0 → Visit Month 2	2 months	49 – 83 
Visit Month 2 → Visit Month 3	1 month	28 – 48 
Visit Month 2 → Visit Year 1	12 months	335 – 395 
Visit Month 2 → Visit Year 2	24 months	700 – 760 
Visit Month 2 → Visit Year 3	36 months	1065 – 1125 
Visit Month 2 → Visit Year 4	48 months	1430 – 1490 
Visit Month 2 → Visit Year 5	60 months	1795 – 1855 
Visit Month 2 → Visit Year 6 	72 months	2160 – 2220 

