**Figure 2 Detailed overview of the 1-Additional Dose, Revaccination and Control groups (Year 1 only)**

§ N = Maximum number of subjects expected for ZOSTER-049 based on the number of subjects in the ZOSTER-006/022 studies.

\* The two groups (1-Additional Dose and Revaccination, only) will have a HZ/su vaccination (Vacc 1) at Visit Month 0 and the Revaccination group will have a second dose (Vacc 2) at Visit Month 2.

\*\* Blood sampling (BS) as in the Sampling schedule (See protocol)

Refer to [Figure 1](#) for study activities beyond Year 1.

† Monthly phone contacts will be done to assess HZ cases and safety follow up for all study groups and will NOT occur when subjects have a scheduled visit.

- Experimental design: Phase IIIb, open-label, multi-centre, multi-country study with 4 groups.
- Duration of the study: Each subject will be followed for approximately 6 years.
- Epoch 001: LTFU of studies ZOSTER-006/022 starting at Visit Month 0 and ending at Visit Year 6 (Month 72) and assessment of 1 or 2 additional doses in two groups of subjects.
- Study groups: The study will be comprised of four study groups as follows:

**LTFU Group:** Subjects from this group [ $N \leq 14,000$ ] will be followed for vaccine efficacy (VE) and safety. In addition, immunogenicity will be followed in subjects that were part of the immunogenicity subset (HI) in the ZOSTER-006/022 studies and Cell-Mediated Immunity (CMI) subset from the ZOSTER-006 study;

**1-Additional Dose Group:** Subjects from this group [ $N = 60$ ] will receive 1 additional dose of the HZ/su vaccine, at the time of enrolment, to assess the immunogenicity, reactogenicity and safety of 1 additional dose;

**Revaccination Group:** Subjects from this group [ $N = 60$ ] will be revaccinated with 2 additional doses of the HZ/su vaccine, on a 0, 2-month schedule from the time of enrolment, to assess the immunogenicity, reactogenicity and safety of 2 additional doses;

**Control Group:** Subjects from this group [ $N = 120$ ] will not be vaccinated but will serve as a control to assess immunogenicity and safety compared to the two vaccinated groups 1-Additional Dose and Revaccination. This Control group will also be used to evaluate the VE, safety and immunogenicity.

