### **4.2. Secondary endpoints**

- Confirmed HZ cases;
  - Confirmed HZ cases since one month post dose 2 in the previous ZOSTER-006/022 studies;
- PHN cases;
  - PHN cases during the ZOSTER-049 study and since one month post dose 2 in the previous ZOSTER-006/022 studies;

- HZ related complications (other than PHN);
  - HZ related complications (other than PHN) during the ZOSTER-049 study and since one month post dose 2 in the previous ZOSTER-006/022 studies;
- Anti-gE humoral immunogenicity at Months 0, 12, 24, 36, 48, 60 and 72 (LTFU HI subset, 1-Additional Dose, Revaccination and Control groups), at Month 1 (1-Additional Dose, Revaccination and Control groups), and at Month 3 (Revaccination and Control groups);
  - Anti-gE Ab concentrations as determined by ELISA;
- CMI in terms of frequencies of antigen-specific CD4+ T cells at Months 0, 12, 24, 36, 48, 60 and 72 (LTFU CMI subset, 1-Additional Dose, Revaccination and Control groups), at Month 1 (1-Additional Dose, Revaccination and Control groups), and at Month 3 (Revaccination and Control groups);
  - Frequencies of CD4+ T cells with antigen-specific Interferon gamma (IFN- $\gamma$ ) and/or Interleukin-2 (IL-2) and/or Tumour Necrosis Factor alpha (TNF- $\alpha$ ) and/or CD40 Ligand (CD40L) secretion/expression to gE as determined by ICS;
- Solicited local and general symptoms in subjects administered with 1 or 2 additional doses of HZ/su vaccine (1-Additional Dose and Revaccination groups);
  - Occurrence, intensity and duration of each solicited local symptom within 7 days (Days 0 - 6) after each vaccination;
  - Occurrence, intensity, duration and relationship to vaccination of each solicited general symptom within 7 days (Days 0 - 6) after each vaccination;
- Unsolicited AEs in subjects administered with 1 or 2 additional doses of HZ/su vaccine (1-Additional Dose and Revaccination groups);
  - Occurrence, intensity and relationship to vaccination of unsolicited AEs during 30 days (Days 0 - 29) after each vaccination, according to the Medical Dictionary for Regulatory Activities (MedDRA) classification;
- Serious AEs;
  - Occurrence and relationship to vaccination of all SAEs;
    - from Visit Month 0 until 12 months: for Control and 1-Additional Dose groups;
    - from Visit Month 0 until 12 months after last HZ/su vaccination: for the Revaccination group;

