## **7.5. Safety and reactogenicity**

### **7.5.1. Counting rule**

The way the percentage of subjects will be derived will depend on the event analysed (see the following table for details). As a result, the denominator (N) will differ from one table to another.

Event	N used for deriving %	Terminology used in the tables for N
Concomitant medication	All vaccinated subjects	Number of subjects with at least one administered dose
Solicited general symptom	All vaccinated subjects with at least one solicited general symptom documented as either present or absent	For each dose and overall/subject: N= number of subjects with at least one documented dose For overall/dose: N= number of documented doses
Solicited local symptom	All vaccinated subjects with at least one solicited local symptom documented as either present or absent	For each dose and overall/subject: N= number of subjects with at least one documented dose For overall/dose: N= number of documented doses
Unsolicited symptom from day 0 to day 29	All vaccinated subjects	Number of subjects with at least one administered dose
SAE/ Related SAE	All vaccinated subjects	Number of subjects with at least one administered dose

Documented dose= symptom screen completed

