### 7.6.4. Unsolicited symptoms

All vaccinated subjects will be considered for the analysis of unsolicited symptoms.

The analysis of unsolicited adverse events, including serious adverse events, consists of evaluating the percentage of subjects with at least 1 report of an unsolicited adverse event classified by the Medical Dictionary for Regulatory Activities (MedDRA).

Subjects who missed reporting unsolicited symptoms will be treated as subjects without unsolicited symptoms.

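### SAP 6.4.1 counts Revaccination about two months longer than Control in the longer-window safety tables, which raises its column mainly for medically attended AEs

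*SAP*

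**What the plan says.** SAP section 6.4.1 plans two sets of longer-window tables for the randomised groups.

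- For SAEs and pIMDs, counting starts at the first vaccination and runs "up to 12 months post last vaccination for 1-Additional Dose and Revaccination group and within 12 months of Month 0 visit for Control group".
- For medically attended unsolicited AEs, the window is "from first vaccination up to 6 months post last vaccination for 1-Additional Dose and Revaccination group and within 6 months of Month 0 visit" in Control.

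The Revaccination window follows the endpoint definition for SAEs and pIMDs in SAP section 4.2, "from Visit Month 0 until 12 months after last HZ/su vaccination: for the Revaccination group". It also follows protocol section 9.1.5 for medically attended visits.

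Protocol Table 6, footnote g, limits collection in the other two groups: "The reporting of medically attended visits will be from Visit Month 0 until 6 months (for the Control and 1-Additional Dose groups"). Footnote h does the same for SAEs and pIMDs at 12 months.

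SAP section 2 says that the Control group "will serve as a control to assess immunogenicity and safety compared to the two vaccinated groups 1-Additional Dose and Revaccination".

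The outputs are per subject. For unsolicited symptoms and SAEs, SAP section 7.5.1 labels the denominator "Number of subjects with at least one administered dose". SAP section 7.6.4 says the analysis of unsolicited events, SAEs included, "consists of evaluating the percentage of subjects with at least 1 report of an unsolicited adverse event". Neither 6.4.1 nor 6.4.2 plans a person-time rate or a common-window table for these events.

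**The concern.** For a Revaccination subject who receives dose 2, the clock starts at dose 1 and stops 12 or 6 months after dose 2. For a Control subject it starts at Month 0 and stops 12 or 6 months later. 1-Additional Dose has the same windows as Control, and so does a Revaccination subject who receives only dose 1. The extra time therefore falls only on dose-2 recipients.

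The window is sensible within the Revaccination group. The difficulty arises when its percentages stand beside those of the randomised comparator without adjustment for time at risk. A higher percentage is then the expected result if the vaccine does nothing, and it could be read as an effect of the second dose. A reader cannot recover common-window percentages from the aggregated tables.

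The 30-day tables avoid this for Revaccination against Control, because Control is counted after both the Month 0 and the Month 2 visit.

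**Working it through.** The documents state no window total and no event rate for these tables, so there is no figure of the plan's own to reproduce.

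**Inputs from the documents**
- Follow-up: 12 months (SAEs, pIMDs) or 6 months (medically attended AEs), from the last dose in Revaccination and from Month 0 in Control (SAP 6.4.1).
- Dose 2: nominally Month 2. Protocol Table 10, "Intervals between study visits for the Revaccination group", allows 49-83 days from Visit Month 0.
- Group sizes: 60 Revaccination, 120 Control (protocol 6.1.1.2.1).

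**Assumptions**
- Constant hazard, complete follow-up and no vaccine effect.
- Control risk p of 10, 30 and 50% for medically attended AEs over 6 months; 5, 10 and 20% for SAEs and 0.5, 1 and 2% for pIMDs over 12 months.
- SAP 6.4.1 literally refers to the percentage of unsolicited AEs that led to a medically attended visit. This is read as a percentage of subjects, following SAP 7.6.4.

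**Step 1: window lengths**, at 30.44 days per month
- SAEs and pIMDs: 12 + 2 = 14 months nominal. The range is 12 + 49/30.44 = 13.6 to 12 + 83/30.44 = 14.7. The nominal ratio to Control is 14/12 = 1.17.
- Medically attended AEs: 6 + 2 = 8 months nominal. The range is 6 + 49/30.44 = 7.6 to 6 + 83/30.44 = 8.7. The nominal ratio is 8/6 = 1.33.

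**Step 2: Revaccination risk with no effect**

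q = 1 - (1 - p)^(W/B), where W is the Revaccination window and B the Control window. Extra subjects = 60 x (q - p). For p = 30% over 6 months: q = 1 - 0.70^(8/6) = 37.8%, the ratio is 1.26 and the excess is 4.7 subjects.

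**Step 3: chance that Revaccination shows the higher percentage.** This uses exact binomials with n = 60 and n = 120. The reference column uses p in both groups; it falls below 0.5 because of ties and discreteness.

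| Event | Control p | q | Ratio | Extra of 60 | P(higher), planned windows | P(higher), equal windows |
|---|---|---|---|---|---|---|
| Medically attended | 10% | 13.1% | 1.31 | 1.9 | 0.69 | 0.46 |
| Medically attended | 30% | 37.8% | 1.26 | 4.7 | 0.84 | 0.47 |
| Medically attended | 50% | 60.3% | 1.21 | 6.2 | 0.90 | 0.48 |
| SAE | 5% | 5.8% | 1.16 | 0.5 | 0.53 | 0.44 |
| SAE | 10% | 11.6% | 1.16 | 0.9 | 0.58 | 0.46 |
| SAE | 20% | 22.9% | 1.15 | 1.8 | 0.65 | 0.47 |

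For pIMDs at 0.5, 1 and 2% the excess is 0.05, 0.10 and 0.20 subjects of 60. At 1% the chances of a higher, lower or tied percentage are 0.38, 0.39 and 0.23, so no direction would be visible.

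**Step 4: sensitivity for medically attended AEs** at p = 10, 30 and 50%
- Dose 2 at day 49 to day 83: 1.5-2.5, 3.8-6.3 and 5.1-8.1 extra subjects.
- If 10% of Revaccination receive only dose 1, the risk is 0.9q + 0.1p. The ratios are 1.28, 1.24 and 1.19; the extra subjects 1.7, 4.2 and 5.6; and P(higher) 0.67, 0.81 and 0.87.

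**Step 5: size against sampling error.** The excesses are 3.1, 7.8 and 10.3 percentage points. The approximate 95% half-widths for the 60 versus 120 difference are 10.1, 14.8 and 15.3 points.

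**The case against.** The strongest reply is that the SAP applies the protocol's declared endpoint. The windows are stated openly and consistently in the protocol and the SAP, each group is tabulated over its own risk period, the analyses are descriptive, and 6.4.1 plans no difference, ratio or test between groups for these events. Harm then requires a reader to compare columns while ignoring a stated window. That limits the consequence, but it does not make the columns comparable, and Control is in the study partly for this safety comparison.

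Several further points stand as limits:
- The expected excess is smaller than the sampling error of a single comparison at these group sizes.
- The medically attended rates are assumed. If the statistic is truly a share of AEs and not of subjects, the ratios above do not apply.
- Table layout belongs to the separate output specification (OPS), which is not available here, so the side-by-side display is inferred from the SAP text.
- SAEs and pIMDs are also listed individually, which helps for those events. No such listing is named for medically attended AEs.
- The 12-month fatal-SAE tables in SAP 6.4.2 use the same group-specific cut-offs and were not sized here.

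A footnote stating the windows would help, but it would not give the reader the common-window figures.

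**Conclusion.** The point holds. The window difference follows directly from the text and is certain for dose-2 recipients. Its effect on the tables depends on the assumed rates.

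The emphasis on medically attended AEs is justified. Their window is 33% longer, against 17% for SAEs and pIMDs. Protocol 9.1.5 also counts any non-routine doctor visit as well as hospitalisation and emergency visits, so these events should be the commoner ones. The order would reverse only in cases such as a 6-month medically attended risk below about 5% alongside a 12-month SAE risk of 10%.

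For SAEs the shift is slight. For pIMDs it can be ignored; protocol 5.3 also excludes subjects with a new or worsened pIMD since first primary vaccination from these groups. This is a systematic, one-directional display bias known in advance. It is not a type I error problem. It should be corrected because the correction is cheap.

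**What to change.** In the between-group tables, present Month 0-12 for SAEs and pIMDs and Month 0-6 for medically attended AEs in all three randomised groups. Control cannot be lengthened to match Revaccination, because its collection of these events stops at 12 and 6 months.

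Keep the protocol-defined window, to 12 or 6 months after the last dose, as a separate Revaccination display. It is still needed because the common windows leave only 9.3-10.4 months (12 - 83/30.44 to 12 - 49/30.44) and 3.3-4.4 months (6 - 83/30.44 to 6 - 49/30.44) after dose 2.

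The data are already collected in all three groups. The cost is a change of table specification and one extra Revaccination display; no data collection or clinical rule changes.
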